- Proportion with a change from a histological diagnosis of definite NASH or indeterminate for NASH to not NASH at end of treatment
- Individual histological characteristics at end of treatment compared to baseline such as steatosis, lobular inflammation, portal chronic inflammation, ballooning, fibrosis score and stage 1a vs. 1b fibrosis
- Change in mean NAS

Study duration (per participant)

- Screening must occur within 90 days of liver biopsy and randomization within 120 days of liver biopsy.
- 52 week treatment period
- 24 week post-treatment follow-up

Study duration (calendar time):

- Recruitment phase: 19 months
- Follow-up phase: 37 months
- Expected rate of recruitment is 16 per clinical center; approximately 2 per month

Number of clinical centers

• 10

4

Randomization: Centrally administered randomization stratified by clinical center

Visit schedule:

- Screening visit must occur within 90 days of liver biopsy and randomization within 120 days of liver biopsy.
- Randomization: Final pre-treatment interview followed by web-based randomization into one of 2 groups to receive either cysteamine bitartrate DR or placebo. The randomization design will be stratified by clinical center and baseline body weight into one of three categories (less than or equal to 65 kg, greater than 65 kg up to 80 kg, or greater than 80 kg) with assignments in permuted blocks of random length within each stratum to achieve a target dose of 9 to 12 mg/kg per day up to a maximum total dose of 600-900 mg per day and dispensing of study drug
- Follow up visits (N=6):
 - 4, 12, 24, 36, and 52 treatment weeks after randomization
 - 76 weeks after randomization (24 weeks after treatment ends)
- Both groups will be administered current standard of care nutrition and exercise recommendations, as a series of one page hand-outs given to participants at randomization and each follow-up study visit (one hand-out per visit). These one-page handouts will include serial strategies to limit screen time, reduce saturated fat, simple carbohydrate and fructose intake, and increase physical activity, as well as fruit and vegetable intake.

Liver biopsy schedule:

- Standard of care biopsy prior to screening for the trial
- 52 treatment weeks after randomization

MRI schedule:

- Prior to treatment initiation
- 52 treatment weeks after randomization (to coincide with liver biopsy when possible)

Statistical Analysis:

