• The primary analysis is an intention-to-treat analysis in which the proportions of subjects in the active treatment group (cysteamine bitartrate DR orally twice daily) with histological improvement in NAFLD (primary outcome, defined above) is compared with the proportion of subjects in the placebo group in whom there is improvement. The comparison is made using a stratified (by clinical site) Mantel-Haenszel chi-square test; a P-value of 0.05 will be considered statistically significant. Subjects who do not undergo an end-of-treatment biopsy will be counted as not improved.

Sample size and assumptions:

- Total of **160** participants in 2 groups of equal size (**80** per group)
- Primary comparison: cysteamine bitartrate DR vs. placebo
- Primary outcome measure: Histological improvement in NAFLD
- Error protection
- Type I = 0.05
 - Type II = 0.10 (90% power)
- Uncorrected chi-square test using Dupont and Plummer, Power and Sample size software (1998)

Design synopsis

- Missing data: 10% will not have 52 week biopsy and will be considered not improved
- Minimum clinically important difference = 33% relative reduction in percent without clinically important improvement in NAFLD in the active treatment group compared to placebo group.
- Allocation ratio of active treatment to placebo groups = 1:1
- Assumed response rates: Expected percent with no clinically important improvement in NAFLD in the placebo group: 75% (based on TONIC data and assumed background use of medications that may influence histology = 33%)
- Expected percent with lack of clinically important improvement in NAFLD in the cysteamine DR group: 50%

Safety Monitoring

• NIDDK-appointed DSMB will monitor the data for safety and efficacy for outcomes such as hepatotoxicity, pregnancy, and any other outcomes or events identified as safety related.

1. Objectives

We hypothesize that administration of cysteamine bitartrate DR for 52 weeks in children with nonalcoholic fatty liver disease (NAFLD) will result in improvement in liver disease severity as measured by changes in the NAS.

The principal objective of this randomized, multicenter, double-masked placebo-controlled trial is to evaluate whether 52 weeks of treatment with cysteamine DR in children improves NAFLD as measured by changes in histology, compared to treatment with placebo.

Secondary objectives include:

- To assess the safety and tolerability of cysteamine DR in children with NAFLD when given for 52 weeks.

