The randomization scheme will assign patients into two groups to receive either cysteamine bitartrate DR or placebo. The randomization design will be stratified by clinical center and baseline body weight into one of three categories (less than or equal to 65 kg, greater than 65 kg up to 80 kg, or greater than 80 kg; with assignments in permuted blocks of random length within each stratum to achieve a target dose of 9 to 12 mg/kg per day up to a maximum total dose of 600-900 mg per day (children with weights exceeding 100 kg will receive a dose of 900 mg per day). This scheme will ensure that the two groups will be balanced by calendar time of enrollment (to minimize secular effects) and by clinic (to minimize clinic-specific effects of differences in patient populations and management).

The randomization plan will be prepared and administered centrally by the Data Coordinating Center (DCC) but will not require real time interaction with a DCC staff member. Requests for randomizations will be made by the clinics using a web-based application. An assignment will be issued only if the database shows that the patient is eligible, has signed the consent/assent statement, and has had all required baseline data keyed into the database.

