7.3 Statistical analysis

Primary outcome measure:

Statistical analyses for the primary hypothesis will follow the intention-to-treat paradigm, which means that all randomized patients with baseline and 52 week liver biopsies will be included in the treatment group to which they were assigned. Any randomized patient who does not have the requisite biopsies will be accounted for and compared by assigned treatment group.

Since the primary outcome measure, defined in Section 7.2, is a binary indicator of improvement in histologic activity score after 52 weeks of treatment compared to baseline and since the randomization is stratified by clinic, P-values will be derived from the Mantel-Haenszel $\chi 2$ test for stratified 2x2 tables. The proportion of patients improved in the group assigned to cysteamine DR will be compared to the group assigned to placebo and a two-tailed p-value of ≤ 0.05 will be considered statistically significant.

Secondary outcome measures:

Statistical analyses for the secondary measures that are continuous measures or scores will be carried out using separate bootstrapped mixed-effects-models corresponding to each individual change measure (defined in Section 7.2) as the response variable, with random effects for variation by clinic, and an indicator variable for comparing cysteamine DR (compared to placebo). The regression coefficient estimate for the indicator variable is the treatment effect for each secondary measure and is interpreted as the mean of the per-patient differences in each secondary outcome measure in the cysteamine DR group minus the corresponding mean differences in the placebo group. Statistical significance for each secondary treatment effect will be achieved if zero is not included in the nominal 95% bootstrapped confidence limits for each secondary measure. Bootstrapping with 2,000 replications will be performed to achieve 95% confidence limits that account for, in advance,

potential non-normality in the continuous secondary outcomes measures or scores. The bootstrapping estimation will be carried out using Stata software.

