7.5 Justification of sample size

A total of 160 participants in two groups of equal size (80 per group) will be included to compare the efficacy of cysteamine DR vs. placebo with the primary outcome measure of histological improvement in NAS (as defined in section 7.2). A sample size of 160 patients with 1:1 randomization would provide 90% power to the study hypothesis to detect a significant difference between the two groups with a two-sided type I error rate of 0.05. This sample size takes into account that 10% of participants will not have 52 week biopsies and will be considered not improved based upon intention to treat analysis. The sample size estimation is based upon the assumption that the minimum clinically important difference, defined as a 33% lower relative rate of no histological improvement in the cysteamine DR group vs. the placebo group, will be expected with the assumed response rates in the placebo group of 75% (based on TONIC data and 2 to 1 split for patients not taking vs. taking vitamin E at the start of the trial) vs. expected percent with no histological improvement in NAS in the cysteamine DR group to be 50%. These sample size estimations are conservative and would have a minimal likelihood of a type 2 error.

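### Randomization is stratified by clinic and three weight bands, but the primary and secondary analyses use clinic only; the test stays valid but becomes conservative if weight is strongly prognostic

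*Protocol*

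**What the plan says.** **Randomization.** Protocol 3.2: "The randomization design will be stratified by clinical center and baseline body weight into one of three categories" (up to 65 kg, above 65 to 80 kg, above 80 kg), with permuted blocks of random length within each stratum. The visit schedule in the Design Synopsis says the same. A separate one-line entry in the Synopsis gives only "Randomization: Centrally administered randomization stratified by clinical center".

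**Primary test.** Section 7.3: "since the randomization is stratified by clinic, P-values will be derived from the Mantel-Haenszel" chi-square for stratified 2x2 tables. Synopsis, Statistical Analysis: "The comparison is made using a stratified (by clinical site) Mantel-Haenszel chi-square test". Neither mentions weight.

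**Secondary outcomes.** Section 7.3 uses the same clinic-stratified test for binary outcomes. For continuous outcomes it uses mixed models with random clinic effects and a treatment indicator, without a weight term.

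The protocol does not say why weight band is left out, or whether it expects weight to predict histological improvement.

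**The concern.** Section 7.3 ties the test to the randomization: the strata of the design are the reason given for the strata of the test. The account of the design is incomplete, so the test departs from the rule used to justify it.

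The statistical consequence is known in direction. Blocking within weight band forces the arms to be nearly balanced on weight, which removes weight-related variation from the true sampling error of the treatment comparison. A variance formula that stratifies by clinic only does not credit that balance. If weight predicts the outcome, the estimated variance is too large, so a nominal 5% test rejects less than 5% of the time under the null and some power is forgone.

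Weight band also fixes the dose and capsule count (3.2 and 3.3), and several secondary outcomes are body-size measures (7.2). A reader of the results will therefore ask for a weight-adjusted analysis. If none is fixed in advance, the choice between two p-values falls after unmasking.

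**Working it through.** **Inputs from the protocol.** "A sample size of 160 patients with 1:1 randomization would provide 90% power" (7.5), 80 per arm. Not improved on placebo: "assumed response rates in the placebo group of 75"%, so 25% improved (7.5). "Expected percent with lack of clinically important improvement in NAFLD in the cysteamine DR group: 50"%, so 50% improved (Synopsis). Level: "a two-tailed p-value of ≤ 0.05 will be considered statistically significant" (7.3). Ten centers averaging 16 patients (Synopsis, 4.1). Ten per cent lack the 52-week biopsy and count as not improved.

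**Step 1: reproduce the stated power.** For the uncorrected chi-square with n per arm and p̄ = (p1 + p2)/2,

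z = [ |p1 − p2|·√n − 1.96·√(2p̄(1 − p̄)) ] / √(p1(1 − p1) + p2(1 − p2)).

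With 0.50, 0.25 and n = 80: (0.25 × 8.944 − 1.96 × 0.6847)/0.6614 = 1.35, so power is 91.2%, against 90% stated. It reproduces.

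If the missing-as-failure rule still has to be applied to those rates, they become 0.9 × 50% = 45% and 0.9 × 25% = 22.5%, and the same formula gives 86.0%. The protocol can be read either way, so both pairs are used below.

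**Step 2: sparsity.** 10 centers × 3 bands = 30 strata; 160/30 = 5.3 patients per stratum, or about 2.7 per arm.

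**Step 3: the test.** In stratum k, with n patients, n1 on active, m improved and a improved on active,

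χ² = [Σa − Σ(n1·m/n)]² / Σ[ n1(n − n1)m(n − m) / (n²(n − 1)) ],

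without continuity correction, compared with 3.84.

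**Step 4: simulation.** 160 patients, 10 clinics, blocks of 2, 4 or 6 within clinic by weight band. The weight effect is an assumption, expressed as a log-odds shift per band. The odds ratio between the extreme bands is exp(2 × shift). Overall improvement rates are held fixed as the shift grows.

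*45% versus 22.5%, weight mix 30/30/40%, no clinic effect (8,000 runs for type I error, 5,000 for power):*

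| Shift | Extreme-band OR | Type I, clinic-only | Type I, clinic × weight | Power, clinic-only | Power, clinic × weight | Power forgone by clinic-only |
|---|---|---|---|---|---|---|
| 0 | 1.0 | 0.047 | 0.046 | 85.7% | 84.4% | −1.3 |
| 0.5 | 2.7 | 0.048 | 0.052 | 85.8% | 85.7% | −0.1 |
| 1.0 | 7.4 | 0.042 | 0.051 | 86.9% | 89.0% | 2.1 |
| 1.5 | 20.1 | 0.028 | 0.044 | 89.3% | 93.5% | 4.2 |

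A separate run at these rates gave clinic-only type I error of 0.049, 0.040 and 0.033, and about 0, 2 and 5 points forgone, at shifts of 0.5, 1.0 and 1.5.

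*50% versus 25%, equal weight bands, no clinic effect (20,000 and 10,000 runs; gaps taken before rounding):*

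| Shift | Placebo improvement by band | Type I, clinic-only | Type I, clinic × weight | Power, clinic-only | Power, clinic × weight | Power forgone by clinic-only |
|---|---|---|---|---|---|---|
| 0 | 25/25/25% | 0.050 | 0.051 | 91.1% | 90.1% | −1.1 |
| 0.5 | 35/24/16% | 0.049 | 0.051 | 91.4% | 91.3% | −0.2 |
| 1.0 | 43/22/9% | 0.041 | 0.049 | 91.4% | 92.8% | 1.4 |
| 1.5 | 51/19/5% | 0.031 | 0.049 | 92.9% | 96.1% | 3.1 |

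**Step 5: sensitivity.** With unequal centers at 50% versus 25% the pattern is the same, except that clinic × weight is slightly worse at a shift of 0.5 (90.3% versus 91.1%). With a clinic standard deviation of 0.3 on the logit scale at 45% versus 22.5% (3,000 runs), the points forgone are −1.5, 0.1, 1.5 and 4.4 at shifts of 0, 0.5, 1.0 and 1.5.

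**Step 6: is sparsity avoidable?** A test stratified by weight alone gave 85.6, 86.9, 90.1 and 94.3% power in the first setting and 91.4, 92.4, 93.9 and 96.7% in the second. It was at or above the clinic × weight test throughout, though no clinic effect was simulated. Weight can therefore be used without 30 small strata.

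**The case against.** The strongest reply is that little is broken. The operative randomization is not in doubt: 3.2 and the Synopsis visit schedule agree. The purposes that 3.2 gives for the scheme are a target dose range and balance over calendar time and clinic; it nowhere calls weight prognostic. At a shift of 0.5, already an odds ratio of 2.7 between extreme bands, nothing is lost. The larger losses need odds ratios of about 7 and 20. Full clinic-by-weight stratification carries its own cost. All of this stands, and it limits the size of the point.

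It does not remove the mismatch. Nor is this detail that can simply be left to an SAP: 7.3 fixes the test and its rationale, so an SAP that added weight would depart from the protocol's stated primary analysis.

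Four stronger readings are tempting and are not supported:

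- *Section 7.3 claims that clinic is the only stratum.* It omits weight. The sentence is incomplete rather than false.
- *The primary test is invalid.* Type I error did not exceed 5% beyond simulation error in any scenario, so a positive result would stand.
- *Power collapses as weight becomes more prognostic.* A steep fall appears if the within-band treatment odds ratio is held fixed and the overall rates drift, to about 43% versus 26% at a shift of 1.5. Most of that fall comes from the smaller treatment difference (17 instead of 22.5 points), not from the choice of strata.
- *Confidence intervals for the secondary outcomes are too wide.* No calculation here covers the bootstrapped mixed models, so no size is claimed for them.

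**Conclusion.** The mismatch between randomization and analysis holds, and so does the direction of its effect. The clinic-only test is valid. It is close to nominal if weight is not or only moderately prognostic, and conservative if weight is strongly prognostic: type I error is about 0.05, 0.04 and 0.03 at shifts of 0.5, 1.0 and 1.5 per band. At 45% versus 22.5%, power forgone against clinic × weight is about 0, 2 and 3 to 5 points; at the protocol's own 50% versus 25% it is about 0, 1 and 3 points. If weight is not prognostic, the 30-stratum test is the worse choice by about 1 point.

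These sizes rest on an assumed weight effect, assumed weight mixes, assumed block sizes and mostly no clinic effect, because the protocol supplies no such figures. Severity is minor to moderate: a cheap correction to a stated rule, not a threat to the trial's conclusion.

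**What to change.** 1. In 7.3, and in the Synopsis randomization and analysis lines, name both stratification factors, in agreement with 3.2.
2. Account for weight band in the primary and binary secondary analyses, in one of two ways. Either stratify the Mantel-Haenszel test by clinic × weight, accepting about 1 point of power if weight turns out not to matter. Or use a less sparse form, such as a model with clinic and weight band as separate terms. The second avoids strata of about 5 patients.
3. Add weight band as a fixed effect in the secondary mixed models.
4. Fix the choice before unmasking. If the clinic-only test is kept as primary, give the reason and prespecify a weight-adjusted sensitivity analysis.

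The cost is wording and one variable already collected for randomization; no extra patients or procedures are needed.

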3.5 Primary outcome measure

Centrally scored and masked assessment of histologic improvement in NAFLD between the baseline liver biopsy and follow-up biopsy after 52 weeks of treatment, where improvement is defined as: (1) decrease in NAS of 2 or more and (2) no worsening of fibrosis.

Justification for performing an end-of-treatment liver biopsy:

NAFLD is a clinicopathologic entity and liver biopsy characteristics are required for the diagnosis of NAFLD, the determination of NASH, and the staging of fibrosis. Currently, there are no non-invasive markers to diagnose or grade NASH. Therefore, a liver biopsy is needed to document improvement or worsening. Several of the histologic features of NAFLD including ballooning degeneration and fibrosis have prognostic significance and predict liver-related deaths in patients with NAFLD. Therefore, documentation of improvement of the pathologic lesions of NASH in liver biopsy is needed to show efficacy in a clinical trial.

Rationale for using the NAS:

The primary outcome measure requires improvement in disease activity after 52 weeks of treatment as determined by liver biopsies pre- and post-treatment. The measure is derived from changes from baseline to the end of treatment in the NAFLD activity score (NAS).⁷⁰ The NAS ranges from 0 to 8 (highest activity) and is calculated as the sum of three components of the standardized histologic feature scoring system for liver biopsies:

- NAS = Steatosis (0-3)
- + Lobular inflammation (0-3)
- + Hepatocyte ballooning (0-2)

The NAS provides a semi-quantitative tool to assess treatment response in a clinical trial. It has been validated and this measure is considered a gold standard in the field. It was utilized to assess the efficacy in the NIDDK PIVENS (IND 69,751) and TONIC (IND 71,217) trials conducted by the NASH CRN.⁴⁸ This would also provide a tool to compare the findings across various treatment trials within and outside the NASH CRN. Therefore, we believe that the NAS provides the most objective and reproducible measurement that is available to assess efficacy of treatment in NAFLD.

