4.2 Inclusion criteria

Patients must satisfy all of the following criteria to be eligible for enrollment:

- Children age 8-17 years inclusive.
- Liver biopsy within 90 days of screening visit and not more than 120 days before randomization.
- Clinical history consistent with NAFLD.
- Definite NAFLD based upon liver histology.
- No evidence of any other liver disease by clinical history or histological evaluation
- A histological severity of NAFLD Activity Score (NAS) \geq 4.
- Sexually active female participants of childbearing potential (i.e., not surgically sterile [defined as tubal ligation, hysterectomy, or bilateral oophorectomy) must agree to utilize the same two acceptable forms of contraception from screening through completion of the study and to complete a pregnancy test at each study visit. The acceptable forms of contraception for this study include hormonal contraceptives (oral, implant, transdermal patch, or injection) at a stable dose for at least 1 month prior to screening, and barrier (condom with spermicide, diaphragm with spermicide). Sexual activity will be ascertained at each study visit for post-menarchal females and if sexually active, subject must verify use of the same 2 acceptable forms of contraception.
- Participants must be able to swallow cysteamine bitartrate DR capsules.
- Written informed consent from parent or legal guardian.
- Written informed assent from the child.

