7.2 Outcome measures

Primary outcome measure:

The primary outcome measure, improvement in NAFLD from the start of treatment to the end of treatment at 52 weeks, is defined for each patient as:

- Improvement in NAS score by 2 or more points, and
- No worsening of the fibrosis score

Secondary outcome measures:

- *Conversion from a diagnosis of NASH to not-NASH.* For the subset of patients with NASH at enrollment, determine the proportion whose 52-week liver biopsy results in a centrally determined histological diagnosis of not-NASH
- *Change in NAS*. Change in NAS, is defined for each patient, as the difference in 52 week vs. baseline NAS scores
- *Specific histologic features.* Changes in specific histological scores, defined for each patient, as the difference in 52 weeks vs. baseline, in the following histological features from centrally scores liver biopsies:
 - **o** Fibrosis
 - o Steatosis
 - Lobular inflammation
 - Portal chronic inflammation
 - **o** Ballooning

Change from stage 1b to 1a fibrosis. For the subset of patients with stage 1b fibrosis at baseline, determine the proportion whose 52-week liver biopsy results in a centrally determined histological diagnosis of fibrosis 1a.

• *Serum aminotransferase*. Change in serum aminotransferase, is defined for each patient, as the difference in 52 week vs. baseline serum aminotransferase

- *Gamma-glutamyl transpeptidase*. Change in serum gamma-glutamyl transpeptidase, is defined for each patient, as the difference in 52 week vs. baseline serum gamma-glutamyl transpeptidase
- *MRI-determined hepatic fat fraction*. Change in MRI-determined hepatic fat fraction is defined for each patient, as the difference in 52 week vs. baseline MRI-determined hepatic fat fraction
- *Markers of oxidation and anti-oxidant status*. Change in markers of oxidation and anti-oxidant status, is defined for each patient, as the difference in 52 week vs. baseline values of the following markers:
 - o Malondialdehyde,
 - o F2alpha-isoprostane,
 - o Total antioxidant capacity, and
 - Oxidized LDL
- *Fasting insulin.* Change in fasting insulin, is defined for each patient, as the difference in 52 week vs. baseline fasting insulin
- *Fasting glucose*. Change in fasting glucose, is defined for each patient, as the difference in 52 week vs. baseline fasting glucose
- *Obesity measures.* Change in obesity measures, is defined for each patient, as the difference in 52 week vs. baseline values of the following obesity measures:

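### The primary test is valid but does not condition on baseline NAS; prespecified adjustment would add about 0 to 5 points of power and remove the effect of chance baseline imbalance

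*Protocol*

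**What the plan says.** The primary outcome in Protocol section 7.2 is binary. It requires "Improvement in NAS score by 2 or more points" together with no worsening of fibrosis. Section 3.5 explains that "The measure is derived from changes from baseline to the end of treatment in the NAFLD activity score". The NAS runs from 0 to 8 (section 3.5) and entry requires at least 4 (section 4.2), so baseline values can lie between 4 and 8.

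Section 7.3 fixes the method: "P-values will be derived from the Mantel-Haenszel" chi-square for stratified tables. Its grounds are that the outcome is binary and that clinic is a stratum of the randomization. The Statistical Analysis part of the Design Synopsis names the same method, a "stratified (by clinical site) Mantel-Haenszel chi-square test".

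Baseline NAS is not a randomization factor either. Section 3.2 says: "The randomization design will be stratified by clinical center and baseline body weight into one of three categories". No passage uses baseline NAS as a stratum or covariate, whether in the primary test, the secondary analyses (7.3) or the missing-data sensitivity analyses (7.4). It serves only as the reference point from which the change is measured.

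**The concern.** A responder endpoint built on change can be expected to depend on where the child starts. A child entering at 4 must reach 2 or less; a child entering at 7 need only reach 5 or less. Selecting children on a semi-quantitative biopsy score also makes regression to the mean stronger at the higher entry scores.

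If baseline NAS predicts improvement and is left out, two things follow. Variation that it could explain stays in the error of the comparison, which costs power. And with 80 children per arm and no balancing on NAS, a chance difference between arms in baseline NAS carries into the estimated treatment effect for the trial at hand. Adding the covariate after seeing such a difference would be post hoc, so the choice has to be made beforehand. Because 7.3 fixes the test completely, the point is not left open for later specification.

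**Working it through.** **Inputs from the Protocol (Design Synopsis, 4.1, 7.5).** Two-sided alpha 0.05; 80 per arm; 75% vs 50% not improved, so 25% vs 50% improved; uncorrected chi-square; stated power 90%; 10 clinics averaging 16 children.

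**Input not in the Protocol.** The correlation rho between baseline NAS and improvement. It is treated as an assumption and shown over a range.

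**Step 1: the plan's own figure.** Power = Φ{[Δ√n − 1.96·√(2p̄(1−p̄))] / √(p₀q₀ + p₁q₁)}, with q = 1 − p.
- Δ√n = 0.25 × √80 = 2.236.
- p̄ = 0.375, so √(2 × 0.375 × 0.625) = 0.6847, and 1.96 × 0.6847 = 1.342.
- √(0.1875 + 0.25) = 0.6614.
- (2.236 − 1.342)/0.6614 = 1.352, so power is 91.2%.

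The stated 90% is reproduced; 77 per arm would be enough.

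**Step 2: gain from adjustment.** A covariate with correlation rho multiplies the residual variance by (1 − rho²), so Δ√n in Step 1 is divided by √(1 − rho²). Worked example at rho 0.3: 2.236/0.9539 = 2.344; (2.344 − 1.342)/0.6614 = 1.515; power 93.5%.

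| rho (assumed) | Power | Gain (points) |
|---|---|---|
| 0 | 91.2% | 0 |
| 0.1 | 91.4% | 0.3 |
| 0.2 | 92.2% | 1.1 |
| 0.3 | 93.5% | 2.3 |
| 0.35 | 94.3% | 3.1 |
| 0.4 | 95.2% | 4.0 |
| 0.45 | 96.1% | 4.9 |

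**Step 3: which rho is plausible?** A simple model was used, all of it assumed: underlying NAS with mean 3.5 to 5 and SD 1.5, rounded to 0–8, entry at 4 or more, improvement rates set to 25% and 50%. The correlation of baseline NAS with improvement was 0.13–0.15 if baseline and week-52 scores correlate 0.9, 0.20–0.25 at 0.7, 0.26–0.33 at 0.5, and 0.31–0.41 at 0.3. Against the table, that is a gain of under 1 point to about 4.

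**Step 4: simulation of actual tests.** 10 clinics of 16; rates 25% vs 50%; 4,000 trials per setting, so the Monte Carlo error is about √(0.91 × 0.09/4,000) = 0.45 points. Assumed baseline NAS 4 to 8: 35/30/20/12/3%.

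| Correlation | Planned test (clinic only) | Clinic-stratified residual test, NAS-adjusted | Clinic × NAS (4–5, 6–8) strata |
|---|---|---|---|
| 0 | 91.8% | 91.7% | 89.3% |
| 0.26 | 90.8% | 92.2% | 90.1% |
| 0.35 | 91.6% | 94.7% | 92.1% |
| 0.46 | 91.4% | 96.1% | 94.3% |

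The residual test's type I error was 4.5–5.6%. When NAS is not prognostic it costs nothing measurable. Crossing clinic with two NAS groups loses about 2 points there, because each cell holds only about 160/(10 × 2) = 8 children.

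A second simulation (3,000 trials per setting; NAS 35/30/20/10/5%) put the planned test's type I error at 4.6–5.3%. A logistic score test with ten clinic terms plus NAS ran at 5.6–6.3%.

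**Step 5: chance imbalance.** With that second distribution the NAS SD is 1.166, so the SD of the difference in arm means is 1.166 × √(2/80) = 0.184, and 2 SD is 0.37 points. Multiplied by the slope of the improvement probability on NAS at the 25% placebo rate, this shifts the risk difference by:

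| Odds ratio per NAS point (assumed) | Shift for a 2-SD imbalance (percentage points) |
|---|---|
| 1.22 | 1.4 |
| 1.49 | 2.6 |
| 2.01 | 4.2 |
| 2.72 | 5.3 |

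The planned difference is 25 points. The slope is steeper near 50%, so under the planned effect the shift would be somewhat larger.

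**The case against.** The case for leaving the plan alone is substantial. The test is valid under randomization, it needs no outcome model, and 7.3 gives a reason for it. The sample size was computed without a covariate and meets its target. The benefit depends on an association that the documents do not report, and at a correlation of 0.2 or less it is about 1 point of power at most. The fibrosis condition, and the rule that counts a missing biopsy as not improved, both weaken the link between baseline NAS and the outcome. All of this stands, and it limits the point to one of efficiency.

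Stronger readings are tempting but not supported:

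- **That the omission leaves the trial short of its stated power.** On the stated rates it does not: 91.2% against 90%. Power falls to 86.0% only if the 10% without a biopsy dilute those rates to 22.5% vs 45% improved. That is a separate question about the sample size assumptions.
- **That chance imbalance threatens the false-positive rate.** The planned test held 4.6–5.3% in simulation. The bias is conditional on the imbalance that happens to occur and is already allowed for in alpha.
- **That the gain is 6 to 8 points.** That takes a correlation of 0.5 (5.8 points on the stated rates, 8.1 on the diluted ones). A correlation of 0.5 needs an odds ratio of about 3 per NAS point, with placebo improvement near 6% at NAS 4 and 84% at NAS 8. Dilution would itself lower the correlation.

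The objection does not show a benefit from leaving out a baseline value already in hand, since the residual form of adjustment cost nothing when NAS was not prognostic.

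**Conclusion.** The point holds as a recommendation to gain precision, not as an error in the planned test. Section 7.3 and the Synopsis condition on clinic alone and leave out the starting value of the outcome. On the stated rates the planned test has about 91% power. Adjustment adds about 0 points at a correlation of 0 to 0.1, 1 at 0.2, 2 to 3 at 0.3 to 0.35, and up to about 5 at 0.45. It also removes a conditional shift of about 1 to 5 percentage points in the risk difference for a 2-SD imbalance in baseline NAS.

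The direction rests on how the endpoint is built. The size rests on the assumed correlation, odds ratios and baseline NAS distribution, none of which the Protocol gives. Type I error is not at issue.

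**What to change.** In section 7.3 and in the Statistical Analysis part of the Synopsis, before unmasking:

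- Make the primary test the clinic-stratified Mantel-Haenszel (score) test applied to residuals from regressing improvement on baseline NAS, entered as a number, and clinic. Use the centrally scored baseline NAS on which the endpoint itself is based.
- Report a standardised risk difference with its 95% confidence interval.
- Keep the unadjusted clinic-stratified Mantel-Haenszel test as a sensitivity analysis.
- Do not cross clinic with NAS strata. Do not use a logistic model with ten clinic terms as the primary test unless its type I error is shown to hold.

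The cost is a sentence in each place and a slightly less simple primary test. No extra data, visits or patients are needed.
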